9.0 Reporting of Adverse Events and Device Deficiencies

9.1 Serious Adverse Events

Once the treating physician becomes aware of a device related adverse event, he/she must report this to the Sponsor, within 24 hours.

Sponsor SAE Contact:

[name]
[contact]
e-mail: [contact]

The report must include a full description of the event. Additional supporting documentation may be requested and should be provided to Sponsor as and when it becomes available. Such documentation includes but is not limited to lab reports, discharge summary, hospital notes, etc.

The treating physician is responsible for reporting all SAEs in accordance with local laws and regulations.

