1.3 Rationale

As outlined above, some hydrogel precursor formulations have previously exhibited undesirable properties including issues with adhesiveness, electrical conductivity and skin irritation. Some of these negative properties are the result of poor polymerisation of the monomer in the hydrogel precursors thereby leaving residual monomer and/or by-products, which can cause or result in the some of these undesirable effects. By adjusting the monomer component of the hydrogel precursor, polymerisation can be enhanced thus reducing the amount of residual monomer and/or by-products remaining and negating negative properties.

The KM10T hydrogel used in the geko™ T3 device is derived from an acrylic acid monomer and has good skin adhesion properties with low skin irritation. A new hydrogel designated KM40C has been developed that promises even lower skin irritation due to zero residual acrylic acid, following replacement of the acrylic acid monomer component of the hydrogel precursor with an acrylamide monomer. KM40C also promises good skin adhesion properties, like those of KM10T used in the geko™

T3 device.

As with KM10T, the new KM40C hydrogel formulation has been tested for safety in humans to current international biocompatibility standards (ISO10993) and subsequently, this new formulation has been used in the development of the geko™ device designated geko™ XT-3.

Both the T3 and XT-3 devices are identical in terms of the therapy they deliver to patients, they differ only in the hydrogel used for adhesion to the skin and although the new formulation promises good adhesion properties, this has not yet been tested in a clinical environment on patients receiving geko™ therapy.

As with the T3 device, the XT-3 device meets recognized, International and European safety standards and is also CE marked for its' indicated use in humans for increasing blood circulation and preventing venous thrombosis in patients known to be at high risk of VTE e.g. stroke patients

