3.0 Study Design

The study will be carried out at one clinical site and will be a non-blinded, non-randomised cohort observation study.

The study objective is to compare how well the geko™ device with a new skin adhesive (geko™ XT-3) sticks to the skin compared to that of the adhesive currently used to stick the current device (geko™ T3) to the skin. The performance of the new adhesive is expected to be at least the same if not better than the current one. This is an observational study or cohort study where the performance of the adhesives is observed and rated. There is no intervention to control the performance of the adhesives. As such, a randomized controlled trial is not required as the protocol does not aim to prove a causal relationship between an intervention and adhesive performance.

To enable a direct comparison of performance, patients will be divided naturally into two sequential groups or cohorts. This will also ensure that the XT-3 and T3 devices are not mixed during routine clinical use.

Group 1 patients will be consented and enter Phase 1 of the study. They will continue their treatment pathway with the geko™ T3 device as per hospital clinical protocol for VTE prevention. Group 1 patients will complete the 10-day, study period, before Group 2 patients are consented and enter Phase 2 of the study. Group 2 patients will continue their treatment pathway as per hospital clinical protocol but with the geko™ XT-3 device.

As both the T3 and XT-3 devices are identical in terms of the therapy they deliver to patients, the treatment pathway for both group 1 & 2 patients will be unaffected. The devices differ only in the hydrogel used for adhesion to the skin. Please see Figure. 4 for a schematic of the patient journey.

[figure not shown]

Figure 4: Schematic diagram of the patient journey for Groups 1 & 2.

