8.4.2 Secondary Efficacy Endpoints

The secondary endpoints are:

- The incidence of adverse events (AEs), incidence of serious AEs (SAEs), incidence of study treatment related AEs, and the incidence of investigational device related AEs

Secondary endpoint data from this observational study will be summarised descriptively. Continuous parameters may include mean, standard deviation, median, minimum, and maximum.

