-------------------------------	-------------------------------	-------------------------------	-------------------------------	-------------------------------	-------------------------------	-------------------------------	-------------------------------	-------------------------------	--------------------------------	--------------------------------

CASE REPORT FORM	BASELINE (DAY 0)			DATE (DD/MM/YYYY)				
STUDY SITE:	THE ROYAL STOKE UNIVERSITY HOSPITAL							
PRINCIPAL INVESTIGATOR:	[name]							
SITE NUMBER	0	2	5	PATIENT NUMBER	0		PATIENT INITIALS	

Has the patient experienced any Adverse Events since signing the Informed Consent?

Yes No

If yes, please comment below:

CRF completed by:

Print Name: _____ Signature: _____ Date: ____/____/_____

To be completed by Principal Investigator:

I am confident that the information supplied in this case record form is complete and accurate data.

Signature: _____ Date: ____/____/_____

Follow-up Day 1 (please note days 1-9 CRFs will be the same)

CASE REPORT FORM		FOLLOW-UP 1 (DAY 1)			DATE (DD/MM/YYYY)	
STUDY SITE: PRINCIPAL INVESTIGATOR:		THE ROYAL STOKE UNIVERSITY HOSPITAL [name]				
SITE NUMBER		0  2  5 	PATIENT NUMBER	0   	PATIENT INITIALS	

How many hours did the patient wear the geko™ device for?					_____ hours
How well did the geko™ device stick to the patient's leg?					
Very Well Remained attached 	Well Detached in small area 	Poorly Detached over large area 	Very Poorly Detached completely 	Not at all Would not stick at all 	

If any level of detachment has been indicated, please provide a comment below:

Did the patient need any additional fixation to keep the geko™ device in position?				
None 	Micropore Tape 	Adhesive Accessory 	OnPulse™ Knee Strap 	

If removed was the geko™ device easily re-applied?				
Yes 	No 	N/A 		

If no, please comment below:

Overall, how comfortable was the geko™ device for the patient to wear?				

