5 There are 11 settings, shown by the number of times the light flashes before a pause. Use the + button to increase the setting and - button to decrease.

When working properly geko will cause a visible movement of the muscles in the lower leg, moving the foot out and up, which should continue throughout the whole treatment.

6 To turn it off, hold + button down for 3 seconds. When the button is held the light will flash quickly and when turned off the flashing will stop.

7 Remove carefully in one piece, to avoid damaging the skin.

If stimulation is not achieved geko can also be fitted in alternative positions, see the website for further details.

► Side Effects

Skin Inflammation or Irritation

In some cases, skin inflammation or irritation can develop in the contact area: either remove the device or re-attach in the alternative fitting positions. If the condition persists or recurs, obtain specialist medical advice before resuming use.

► Warnings

Seek specialist medical opinion if the patient is/has:

- Implanted electronic devices (e.g. a cardiac pacemaker).
- Recently diagnosed or suspected DVT.
- Pregnant or breastfeeding.
- Diagnosed heartcondition.
- Epilepsy.
- Had recent surgery where muscle contractions may disrupt the healing process.
- Used the device for 28 consecutive days.

Do not use:

- During any activity in which involuntary muscle contractions may put the user or others at risk of injury (e.g. Driving or operating machinery).
- When bathing or showering – switch off the device and remove temporarily.
- If the device has been worn by another individual – this will carry risk of infection.
- If packaging is open or damaged.
- If device is damaged.

Device should not be used on the following areas of the body:

- Head.
- Eyes.
- Mouth.
- Neck (especially the carotidsinus).
- On the chest, upper back or crossing over the heart. This may increase the risk of cardiac fibrillation.

Do not apply over or near the following:

- Sore, infected or inflamed areas, broken skin or skin eruptions, e.g. phlebitis, thrombophlebitis, varicose veinsetc.
- Cancerouslesions.

Do not use in proximity of the following equipment/environments (which could result in the possible degradation of the performance of geko):

- Short wave/ microwave equipment (i.e. within 1m).
- Portable RF communications equipment (including peripherals such as antenna cables and external antennas) (i.e. within 30cm).
- Heat sources, such as fires or radiant heaters.

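### Two of the four secondary endpoints depend on a relatedness judgement that has no criteria and no CRF field, made by staff who know which gel is in use

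*Combined protocol and SAP*

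**What the plan says.** - **Endpoints.** Sections 2.1.2 and 8.4.2 list four secondary endpoints: the incidence of AEs, the incidence of SAEs, and the "incidence of study treatment related AEs, and the incidence of investigational device related AEs". All four are to be summarised descriptively; no test is planned.
- **Relatedness.** Section 9.1 is the only text that connects anyone with a device-related event: "Once the treating physician becomes aware of a device related adverse event, he/she must report this to the Sponsor, within 24 hours". There are no relatedness categories or causality criteria, no masked assessor, and no explanation of how the two related-AE endpoints differ.
- **Design.** Section 3.0 states that the study "will be a non-blinded, non-randomised cohort observation study", and that "Group 1 patients will complete the 10-day, study period, before Group 2 patients are consented and enter Phase 2 of the study".
- **Expectation.** Section 1.3: "A new hydrogel designated KM40C has been developed that promises even lower skin irritation due to zero residual acrylic acid".
- **Data capture.** The Day 0 and Day 1-9 forms in Appendix 3 ask "Has the patient experienced any Adverse Events since signing the Informed Consent", answered yes or no with a free-text comment. They have no item for relatedness or for the site of the event. The Day 10 form and Section 4.3 have no AE item, although Table 1 marks AE assessment for Days 1-10.
- **Known effect.** Appendix 4 warns: "In some cases, skin inflammation or irritation can develop in the contact area".
- **Related items.** The same forms record comfort on a five-level scale and any additional fixation (tape, adhesive accessory or knee strap).

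**The concern.** An incidence of related events is the product of two things: how often events occur, and how often they are called related. Nothing in the plan holds the second factor constant between phases. Each phase uses one device, the daily form carries the device tick as well as the AE question, and the protocol tells staff what to expect of the new gel. The same patch of redness could be put down to the device more readily in one phase than in the other. The drift could run either way: the stated expectation favours KM40C, while an unfamiliar device may be blamed more readily than one already in routine use.

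At stake is the comparability of two rows of the safety summary. With no relatedness field, those rows must be rebuilt from free-text comments or from physicians' reports, so a reader could not see afterwards whether a difference reflects the skin or the labelling.

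**Working it through.** The plan gives no expected AE rate and no attribution rate, so there is no figure of its own to reproduce. The check takes the cohort size from the plan and assumes the rest.

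**Inputs**
- n = 20 patients per phase (Section 3.2).
- Phase 1 is T3 and Phase 2 is XT-3 (Sections 3.0 and 6.1, and the CRFs). Section 8.3 prints the two groups the other way round. That is a separate matter to reconcile, and the argument here does not depend on it.
- q = true risk of a contact-area skin event, the same in both phases. Assumed: 20%, range 10% to 40%.
- a1, a2 = share of such events called related in Phase 1 and Phase 2. Assumed: 80% v 60%, with wider gaps as variants.

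**Formula.** Expected related count = n × q × a. The apparent Phase 2 to Phase 1 ratio is a2/a1, whatever q is.

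**Results at q = 20%, no true difference**
- 80% v 60%: 20 × 0.2 × 0.8 = 3.2; 20 × 0.2 × 0.6 = 2.4; ratio 0.6/0.8 = 0.75.
- 90% v 50%: 20 × 0.2 × 0.9 = 3.6; 20 × 0.2 × 0.5 = 2.0; ratio 0.56.
- 80% v 40%: 3.2 and 20 × 0.2 × 0.4 = 1.6; ratio 0.50.
- Reversed, 60% v 80%: 2.4 and 3.2; ratio 1.33, an apparent harm.

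**Range over q, 80% v 60%.** At q = 10%, 1.6 v 1.2; at q = 40%, 6.4 v 4.8. The gap is 0.4 to 1.6 patients.

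**Chance that Phase 2 shows fewer related cases** (two independent binomials, n = 20, probabilities q × a1 and q × a2)
- No shift (80% in both): 0.41 at q = 20%; 0.38 to 0.43 for q = 10% to 40%.
- 80% v 60%: 0.55 at q = 20%; 0.47 to 0.65 over the range.
- 80% v 40%: 0.71 at q = 20%; 0.57 to 0.85 over the range.

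**Precision.** The exact 95% interval for 2/20 is 1.2% to 31.7%, and for 4/20 it is 5.7% to 43.7%. Counts of this size cannot separate a shift in attribution from a real change.

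**Same inputs without attribution.** A count of all contact-area skin events has expectation 20 × 0.2 = 4.0 in both phases, whatever a1 and a2 are. That holds only if events are recorded equally often in the two phases.

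**The case against.** The case on the other side is substantial, and much of it stands.

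- **Section 9.1 assigns no causality assessment.** A reader might infer that the protocol hands the judgement to the treating physician. It sets only a 24-hour reporting duty. Under Section 10.0 the CRFs are completed by delegated members of the healthcare team, and the forms are signed by the Principal Investigator. The documented gap is that relatedness is neither defined nor captured.
- **Irritation is neither an objective nor a named endpoint.** The aim is adhesion, the secondary data are descriptive, and Section 1.3 is background. This limits the consequence. A descriptive incidence can still mislead, and here no other item would show why it moved.
- **Other tolerability data exist.** A reader might take the related-AE rows as the only tolerability information tied to the device. They are not: comfort is rated at every assessment, and all-AE incidence needs no attribution. Both are partial checks. Comfort does not identify a skin reaction, and in acute stroke inpatients the all-AE count may hide a few contact-site events.
- **The rates are assumed and the gaps small.** This is correct. Even with no shift, Phase 2 would show fewer related cases about four times in ten.
- **Location is not the same as causation.** It is tempting to go further and redefine device-related as anything in the contact area. Appendix 4 does not support that: it says irritation can develop there, not that every event there is due to the device. The redefinition would also drop non-skin device events from the endpoint and would count reactions to tape, accessory or strap, whose use may itself differ by gel.

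**Conclusion.** The point holds as a limited weakness of the safety summary. Two of the four secondary endpoints rest on an undefined, unrecorded and unblinded judgement, so a change in attribution between phases scales them by a2/a1 with no change in true events. Under the illustrative assumptions (20% true risk in both phases, 80% v 60% attribution) that is 3.2 v 2.4 of 20; the real size and direction are unknown.

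A reader might infer that the study is set to show a false irritation advantage for XT-3. The documents do not support that: no irritation claim is planned, drift could run either way, and with 20 patients per phase these counts could not carry such a claim in any case. Attribution plays no part in the primary adhesion comparison.

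**What to change.** 1. Keep both related-AE endpoints as they are, including non-skin device events, and add a relatedness item to the AE section of the CRF.
2. Add one descriptive row to Section 8.4.2: every skin AE within the device contact area on either leg, counted regardless of attribution and by the same rule in both cohorts, shown beside the attributed incidences.
3. Add one tick, *within device contact area: yes/no*, beside the AE question on every CRF. Put the AE question and the tick on the Day 10 form too, and bring Section 4.3 into line with Table 1.
4. Show the new row split by use of additional fixation, which the forms already record. The split is descriptive only, because fixation may depend on how well each gel sticks.

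The rule should be set before Phase 1 data are collected, since location may not be recoverable from free text.

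**Cost.** A relatedness item, one tick, the AE question on the Day 10 form, and one table row; no extra patients or visits. **Downside.** Some events caused by stockings, compression or fixation will be counted. The decision to record an event at all remains unblinded, so the row removes drift in attribution but not drift in recording, and it does not address the sequential cohorts.

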9.2 Device Deficiencies

Any device deficiencies should be reported via Firstkind's proprietary complaints system.

10.0 Direct Access to Source Data / Documentation

Data will be collected on paper case report forms (CRFs) by appropriately trained delegated members of the patient's healthcare team at the clinical site. Only designated members of the team will be allowed to record and / or correct data in the CRFs. CRFs

will be provided by the Sponsor to the site for completion together with CRF completion guidelines. All CRFs for the study, can be found in Appendix 3 of this protocol. Patients will be assigned a unique study identification number (participant number and initials) and will be identified only by this unique identifier on CRFs and on source documents by name and date of birth. No personal identifier will be used in any publication or communication used to support this research study. The participant identification number will be used if it becomes necessary to identify data specific to a single participant. The monitors, auditors, personnel authorised by the Sponsor, the local IRB, and regulatory agencies are eligible to review medical and research records related to this study as a part of their responsibility to protect human participants in clinical research and will be given direct access to source data and documentation (e.g., medical charts/records, printouts etc.) for source data verification, provided that participant confidentiality is maintained in accordance with local requirements. Access to electronic medical records may be governed by institution policy and each site will be required to ensure access while remaining compliant with institutional requirements.

11.0 Quality Control and Quality Assurance

11.1 Monitoring Requirements

In order to maintain knowledge of the progress of a study, the Sponsor's designated Clinical Research Associate (CRA) / monitor will visit the centres during the study as well as maintain frequent telephone and written communication. The Investigator will permit the Sponsor to monitor the study as frequently as is deemed necessary and provide access to medical records to ensure that data are being recorded adequately, that data are verifiable, and that protocol adherence is satisfactory.

The Investigator will permit representatives of the Sponsor and/or designated CRO to inspect all pCRFs and corresponding study participant original medical records (source documents) at regular intervals throughout the study. Participant original medical records and other relevant data must be available to support all data recorded in the CRF. In addition to the original medical records, these data may include but is not limited to, study, laboratory and diagnostic reports, wound images and tracings, quality of life questionnaire, etc.

Site inspections serve to verify strict adherence to the protocol and the accuracy of the data being entered on the CRFs, in accordance with applicable regulations. A Monitoring Log will be maintained at each study site which the monitor will sign, date and state the type of visit.

The Investigator should be aware that the study site and participant records might be inspected and audited by the Sponsor or representatives of Sponsor or relevant regulatory authorities.

11.2 Acceptability and Storage of Case Report Forms

A CRF must be completed for each participant who has signed an informed consent form. All source documents and CRFs will be completed during or as soon as possible after the patient's assessments have been completed. The Investigator will review the

CRFs to indicate that, to his / her knowledge, they are complete and accurate. CRFs will be reviewed by the Sponsor's CRA / Monitor, at the time of a monitoring visit, for adherence to completion guidelines and verified against source documents.

Verified / corrected CRFs will then be photocopied and submitted to the Sponsor, leaving the original copies of the CRFs

at the site e.g. CRA / Monitor may hand carry completed CRFs to the Sponsor. If data is not retrieved at the time of the monitoring visit, the Sponsor may want copies of the CRFs submitted via Email or mail. As patients will be identified only by a unique study identification number (participant number and initials), the CRFs are already fully anonymized prior to being sent to the Sponsor. It is the responsibility of both the Investigator and the Sponsor to ensure that all CRFs are stored in a secure location during the course of the study and archived when the study has finished.

11.3 Protocol Amendments

A modification or alteration to this protocol may not be undertaken without first obtaining the concurrence of Sponsor. Both the Lead Investigator and the Sponsor representative must sign and date the amendment prior to implementation. In addition, the Lead Investigator must report all protocol amendments to, and receive all required approvals from, the Institutional Review Board / Independent Ethics Committee (IRB / IEC) PRIOR to implementation of any protocol amendment at the study Centre, with two exceptions:

1. When necessary to eliminate apparent immediate hazard to the participant; or
2. When the modification involves only logistics or administration.

If a protocol change is proposed for all participants, the following procedure for a protocol amendment will be followed. An amendment must be in writing and it must be dated by both the Sponsor and the Investigator. If necessary, the Sponsor will submit protocol amendments to the appropriate regulatory authorities and notify other Investigators using this protocol.

An amendment may also require modification of the informed consent form. The Investigator will provide an approval letter for the amendment and revised informed consent form, if applicable, to the Sponsor.

Any protocol amendments will be listed in the "Appendices" portion of the Table of Contents.

